# Table 10. Overview of outcome domains and prioritized hierarchy of outcomes Outcome domain Specific outcome variables

		Primary outcome		
Sport function	1.	KOOS-child 'Sport/play' 0-100 subscale (7 items)		
		Secondary outcomes		
Patient-acceptable Symtom- state	2.	PASS question (Y/N)		
Knee-related Quality of Life	3.	KOOS-child 'Quality of Life' 0-100 subscale (5 items)		
Pain intensity and frequency (Pain flares)	4.	4-week-average episodes of pain flares (≥4 on 0-10 NPRS)	11.	KOOS-child question P1 on 'Pain' subscale (1-5 Likert scale)
	5.	Worst pain past week (0-10 NPRS)	12.	Level of pain/discomfort (EQ-D5-Y 4)
Participation in sports and physical activity	6.	4-week average hours of sports participation	13. 14. 15. 16. 17.	4-week average hours of MVPA Satisfaction with extent of sports participation Pre knee pain level of sports participation Pre knee pain level of physical activity Time to return to sport (week no.)
Osgood-Schlatter morphology (ultrasound imaging)	7.	Flaviis composite severity score	18. 19. 20.	Tendinosis signs (thickening or hyperemia) Infrapatellar bursitis signs (effusion or hyperemia Hyperemia of the tibial tubercle ad modum Öhberg
Pain during knee loading	8.	Anterior Knee Pain Provocation test (0-10 NPRS)	
 
21.
 
22.
 
23.
 
24.
 
25.
 
	Pain during knee extension test (0-10 NPRS) Pressure-pain threshold at the tibial tubercle (kPa) KOOS-child 'Pain' 0-100 subscale (8 items) Known pain during manual palpation Pain during countermovement jump (0-10 NPRS)
Objective knee function			26. 27. 28. 29.	Maximal isometric knee extension strength (Nm/kg) Countermovement jump height (cm) Countermovement power (W) Knee extensor flexibility change (°)
Global rating of change	9.	7-point Likert scale	30.	Satisfaction with treatment (Y/N)
Usual activities	10.	Patient-specific function scale (NRS 0-10)	31.	Problems with usual activities (EQ-D5-Y 3)
Pain beliefs			32.	Kinesiophobia (Tampa Scale of Kinesiophobia, 17 items)
Health			33.	Self-rated health (EQ-D5-Y 0-100 VAS)
		Safety outcomes		
	1.	Any adverse events		

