## Sample size considerations {14}

The properties of the primary outcome measure KOOS-child and the "Sport/rec" subscale have been well investigated, with a validation study including adolescent participants with Osgood-Schlatter amongst other overuse- and acute knee disorders. A small cohort of patients in our clinic (n=16) who 1) were eligible for inclusion in the trial at baseline, 2) received the intervention in question and 3) attended follow-up, reported their global rating of improvement on a 7 point Likert scale ranging from 'much worse (7)' to 'much better (1)'. Patients who reported 'much better (1)' or 'better (2)' had a mean improvement on KOOS-child

'Sport/play' subscale of 12.7±16 points, whereas patients reporting less improvement ('little' improvement or 'no change') only had a 3.57 point increase. In absence of more robust specific data in terms of severity, intervention, and length of follow-up, we will utilize this 9 point difference as a threshold for determining superiority. We consider this to be a meaningful change and a relevant between-group difference, and is within the recommended range of 8-10 points (heartbeat-med.com/resources/knee-injury-and- osteoarthritis-outcome-score-koos). This change also exceeds the smallest detectable group-level change (2.66 points) and the standard error of measurement (8.02 points).

In order to detect such a change with a standard deviation of 16 points an  $\alpha$  level (type I/false positive error rate) of 5% and power ( $\beta$ -1, or probability of avoiding type II/false negative error rate) of 90%, 55 (54.8) participants per group would be needed based on an independent one-sided t-test (R 4.0.2, Foundation for Statistical Computing, Vienna, Austria; RStudio 1.0.153, power.t.test package). To account for a potential 15% dropout rate a total of 130 participants will be included.

This will correspond to a 0.56 Cohens d 'medium' effect size at 90% power (figure 3). The smallest effect size reliably detectable will thus be >0.482 (Cohens d 'small' effect size) at  $\geq$ 80% power (Jamovi 1.2.25, jpower module), surpassing the trivial (<0.2) and small (>0.2) effect size thresholds. We also consider this sample size to be operationally feasible within the given timeframe and with the resources available to our group.

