### Superiority framework and controlling error rates

The analysis will be evaluated based on a one-sided hypothesis as the trial employs a superiority design, meaning that if a one-sided test of significance fails in the direction of the experimental group, the null-hypothesis is rejected for our sample, and the level of significance in opposite direction is therefore not of interest. To further safeguard this choice, we have made the decision to obtain 90% power (up to 94.6% if all participants retained), corresponding to a 10% false negative error rate). By default, we will not perform adjustments for multiple comparisons as we have arranged our hypotheses in a prioritized order, and we will also conduct and report hypotheses testing in this pre-specified order. We will however adjust for multiple comparisons using Bonferroni corrections when multiple tests are performed for outcomes within the same construct or objective (e.g. the effect of group on acute pain response during loading, measured through 2 different outcomes: pain [0-10 NPRS] during maximal isometric knee extension test, and pain [0-10 NPRS] evoked from the Anterior Knee Pain Provocation test).

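### The prioritised testing order has no stop rule, so it does not control false positives among the secondary outcomes, and the Bonferroni exception leaves its families undefined

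*Combined protocol and SAP*

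**What the plan says.** The section Superiority framework and controlling error rates states the default: "we will not perform adjustments for multiple comparisons as we have arranged our hypotheses in a prioritized order". It adds that tests will be carried out and reported in that order. The Outcomes section describes the order in the same way, as the sequence for testing, analysis and reporting. It intends all primary and secondary outcomes for the primary report. Neither section makes a test conditional on the result of an earlier one. The stopping rules mentioned under Interim analyses concern early termination of the trial, not the test sequence.

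There is one exception. Bonferroni will be applied when several tests address outcomes that share a construct or an objective. The example is acute pain on loading, "measured through 2 different outcomes": pain during the knee extension test and pain from the provocation test. In Table 10 the domain "Pain during knee loading" holds six outcomes (nos. 8 and 21–25).

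The error level appears only in the sample size section ("type I/false positive error rate) of 5% and power"). Testing is one-sided: "The analysis will be evaluated based on a one-sided hypothesis as the trial employs a superiority design". No separate level is given for secondary outcomes. The dissemination section bases the main conclusion on the primary endpoint.

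**The concern.** A fixed order protects the error rate because testing stops at the first failure. Without that condition, ranking only decides which p-value is printed first, and each secondary test keeps its own full chance of a false positive. The reason given for not adjusting therefore does not support the choice.

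The Bonferroni exception could limit the damage, but the plan does not say what forms a family. One outcome could face quite different thresholds, all compatible with the text, and the divisor could be settled once results are known.

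At stake is how the secondary results in the primary report are read. They will carry exact p-values, and Table 10 is titled a prioritised hierarchy. A reader could take significant secondary results as protected by that hierarchy when they are not.

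**Working it through.** **1. The plan's own figure.** The documents state no familywise error rate, so the check starts with the level in use. Inputs are the difference ("we will utilize this 9 point difference as a threshold for determining superiority"), the spread ("with a standard deviation of 16 points"), one-sided 5% and 90% power.

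- Normal approximation: n = 2 × (1.645 + 1.282)² × (16/9)² ≈ 54.2, so 55 per group. The exact one-sided t-test gives 54.82. The plan states 54.8, rounded to 55.
- Dropout of 15%: 110/0.85 = 129.4, so 130, as stated.

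The plan therefore works at one-sided 5%. Using that level for secondary outcomes is an assumption.

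**2. The tests counted.** Outcomes 2–10 of Table 10 are taken as secondary: nine tests in eight domains, with only nos. 4 and 5 sharing a domain. This split is an assumption, because the extracted text of Table 10 does not show where exploratory outcomes begin. The full domain sizes for nos. 2–10, in order, are 1, 1, 4, 4, 6, 4, 6, 2 and 2.

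**3. Chance of at least one false positive, all nulls true, independent tests.** The formula is 1 − ∏(1 − αᵢ).

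- No adjustment: 1 − 0.95⁹ = 37.0%.
- Bonferroni within domains, counting only the tests run (0.025 for nos. 4 and 5, 0.05 for the other seven): 1 − 0.95⁷ × 0.975² = 1 − 0.6983 × 0.9506 = 33.6%.
- Bonferroni counting every outcome in the domain (two tests at 0.05, three at 0.0125, two at 0.0083, two at 0.025): 1 − 0.9025 × 0.9630 × 0.9834 × 0.9506 = 18.8%.

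**4. Correlated tests.** Simulation of equally correlated normal test statistics, 400,000 draws, nine tests. The correlations are assumed; the documents give none.

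| Assumed correlation | No adjustment | Bonferroni within domains, tests run |
|---|---|---|
| 0.3 | 29% | 26% |
| 0.5 | 23% | 22% |
| 0.7 | 18% | 16% |

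The full-domain reading was calculated only under independence. Positive correlation would bring it below 18.8%.

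**5. What the Bonferroni exception could mean.**

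- The example, two outcomes: 0.05/2 = 0.025.
- The Table 10 domain, six outcomes: 0.05/6 = 0.0083.
- The Table 1 objective on patient-reported outcomes, at least 13 legible outcomes: 0.05/13 = 0.0038 or lower.

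PASS shows the spread. It is the first secondary outcome and the basis of the planned Fragility Index. Alone in its Table 10 domain, it is tested at 0.05. Under the Table 1 objective the threshold is 0.0038 or lower.

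**6. With a stop rule.** Any false rejection requires rejecting the first true null in the sequence, which happens with probability at most 5%. The familywise rate over the primary and outcomes 2–10 is then at most 5%.

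**The case against.** The strongest reply is that the trial has one primary outcome at one timepoint, tested first, and rests its conclusion on it. Later tests do not inflate that error. Leaving secondary outcomes unadjusted behind a single primary is a defensible choice if they are labelled supportive. The plan also never claims a fixed-sequence procedure, and it cites sources for its approach that cannot be checked here. The point about the primary stands in full, and it limits the problem to the secondary outcomes. The rest does not rescue the wording: the order is offered as the reason for not adjusting, under a heading about error control, and nothing labels secondary results as supportive.

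The error rates also depend on conditions. They are the chance of at least one false positive when no outcome has a true effect, not the share of positive findings that are false. Many outcomes are overlapping pain and function measures in the same participants, so the independence figures are upper values. At one-sided 2.5% the unadjusted figure for nine tests would be 20%. These points stand and are reflected in the range given.

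A reader might also run the sum over all 32 outcomes after the primary, 1 − 0.95³² = 80.6%, and conclude that false positives among secondary outcomes reach 81%. The documents do not support that. The sum ignores the Bonferroni exception, which under Table 10 domains brings it to 42.8% under independence. On the split assumed here it also pools exploratory outcomes with secondary ones, and only primary and secondary outcomes are intended for the primary report.

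Finally, a mandatory stop rule is heavier than needed, since PASS, a binary outcome, stands second and could block everything after it. That is fair, so the fix offers an alternative.

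**Conclusion.** The point holds for the secondary outcomes. The prioritised order, as written, gives them no error control and does not justify leaving them unadjusted. For outcomes 2–10 the chance of at least one false positive is about 34% under independence with Bonferroni applied within Table 10 domains to the tests run, and about 16–26% with assumed correlations of 0.3–0.7. On that reading it is roughly three to seven times the nominal 5% (16/5 = 3.2; 34/5 = 6.8). Counting every outcome in the domain gives about 19% under independence. All figures assume one-sided 5% for secondary tests, every null true, and nos. 2–10 as the secondary set.

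Separately, the Bonferroni families are not fixed, and the text allows thresholds from 0.025 to 0.0083 for the plan's own example.

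It would go too far to infer that the order controls nothing at all or that the primary result is at risk. The primary is a single test, done first, and it carries the main conclusion.

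**What to change.** Amend the SAP wording before unblinding, in one of two ways:

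- **Make the order operative.** Test the primary outcome, then outcomes 2–10 of Table 10 in order at the same level, and end formal testing at the first non-significant result.
- **Or drop the claim of control.** State that all secondary results are unadjusted and supportive, with no confirmatory significance claim.

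In both cases, report outcomes 11–33 as estimates with intervals. Either delete the Bonferroni exception or fix its families in advance, for example as the Table 10 domains. Under the stop rule the exception is no longer needed.

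The cost is wording only; no data or participants are added. Under the first option, a non-significant early outcome such as PASS removes formal claims for all outcomes after it. Under the second, no secondary outcome can carry a confirmatory claim.

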### Interim analyses {21b}

No interim analyses or stopping rules are planned, due to very low safety concerns and to preserve statistical power. However, an evaluation of feasibility outcomes will be performed after including n=15 participants to decide if potential study amendments will result in these 15 participants being included in the primary dataset (see "Embedded pilot study" section).

## Methods for additional analyses (e.g. subgroup analyses) (20b)

Besides the sensitivity analyses otherwise specified (covariate adjusted, mixed-effects, moderation, mediation), we will perform per-protocol analyses to test the robustness of the primary intention-to-treat analysis, by examining the effect of adherence according to the pre-specified compliance criteria.

## Handling of non-adherence and any statistical methods to handle missing data {20c}

Assuming that data will be missing at random, multiple imputations using chain equations will be used to handle missing data. Imputation models for missing variables will be fitted using linear, logistic or polytomous regression models. All available variables will be included in the imputation models, unless a specific reason is given for exclusion. Imputation will only be performed for variables included in the

[figure not shown]
analysis. Multiple imputation will be done using R-package mice[].

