## Effect moderation and mediation

As secondary analyses, we will perform moderation and mediation (if a superior treatment response in arm A is observed) analyses, which will be conducted and reported in accordance with the AGReMA Statement. Through mediation analysis, the total effect of exposure to treatment groups 1 vs A (i.e. between-group difference) on the outcome, will be parsed into indirect effect pathways from exposure to mediator, and from mediator to the primary outcome (KOOS child 'Sport/play' subscale), which are the effects of interest in this mediation analysis (figure 4). This will allow inference about the underlying responsible mechanisms for a potential effect. Such knowledge is key when optimizing or developing treatments, and for implementation efforts. As the sample size is not planned specifically for mediation analysis, these analyses are considered secondary and should be interpreted with caution mainly based on its effect size and precision. Although potential limitations of suboptimal power, this mediation analysis provides a novel preliminary step for potential identification of causal mechanisms for improvement in Osgood-Schlatter patients.

Mediators are represented by variables measured after randomization and before collection of outcome data, which are thought or known to be influenced by the treatment allocated to participants. As large-scale randomization balances known and unknown confounders that can potentially influence the outcome as well as the exposure-mediator pathway, randomized trials are the optimal setting to perform causal mediation analysis.

The assumed cauasal model we are investigating is illustrated as a directed acyclic graph below (figure 5) using the Dagitty software.

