### Statistical approach to mediation analysis

Mediation analysis will be based on interventional effects, this will allow for the inclusion of multiple mediators and account for dependence between mediators. With estimation done by Monte-Carlo based regressionmodels.Covariates will be included as moderators in the full model. For each mediator, we will calculate and report effect size as odds ratios and p-values, as well as 95% confidence intervals We will calculate and report estimated effect and percentage contribution to total effect for each mediator variable included in the final model, based of the mean indirect effect. The model will only include mediators that fulfill the temporal sequence of a causal relationship, that is exposure, mediator, outcome.

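### The imputation plan does not say how treatment-by-moderator effects are kept, so the planned moderation estimates may be biased towards zero

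*Combined protocol and SAP*

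**What the plan says.** The section on non-adherence and missing data ({20c}) sets out chained-equation imputation in the R package mice, under a missing-at-random assumption. On the form of the models it says: "Imputation models for missing variables will be fitted using linear, logistic or polytomous regression models". Every variable on hand enters as a predictor unless there is a reason to leave it out, and only variables that are part of the analysis are themselves imputed. Product terms, imputation within arm and compatibility with the analysis model are not mentioned, and none of them is ruled out.

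Moderation is planned in several places:

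- *Secondary aims* includes finding out who benefits more or less from treatment.
- *Methods for additional analyses* lists moderation among the analyses already specified.
- *Effect moderation and mediation* says: "As secondary analyses, we will perform moderation and mediation".
- *Statistical approach to mediation analysis* adds: "Covariates will be included as moderators in the full model".
- Table 12 lists the candidate moderators, most of them measured at baseline.

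**The concern.** A moderation analysis estimates how far the slope of outcome on moderator differs between arms. If a missing month-5 score is imputed from a model with group and moderator as main effects only, the imputed score follows one common slope whichever arm the participant is in. Among imputed participants the slope difference is then zero by construction. Pooling them with observed participants dilutes the estimate in one direction, towards no moderation.

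The plan's own wording leads there. A list of variables entered into linear, logistic or polytomous models gives main effects unless products are requested. With 130 participants the interactions are imprecise in any case. The section on moderation and mediation asks readers to weigh the mediation results mainly by effect size and precision, and effect size is what this bias distorts.

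**Working it through.** **The plan's own figures.** The sample-size section states that "55 (54.8) participants per group would be needed based on an independent one-sided t-test", for 9 points and an SD of 16, with alpha 5% and power 90%. The normal approximation is n = 2 × (1.645 + 1.282)² × 16² / 9² ≈ 54.1, rounded up to 55. The exact one-sided t-test gives 54.82, which matches. Inflating for 15% dropout, 110 / 0.85 = 129.4, so 130 in total and 65 per arm. The plan states no figure for attenuation of interactions.

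**Inputs.**
- From the documents: 65 per arm, SD 16, main effect 9 points.
- Missing fraction f: 15% (planning dropout, sample-size section) or 20% (3 of 15 in the pilot, Table 3). Both are stand-ins, because the main-trial fraction is not reported.
- Assumed: a standard-normal moderator and a true interaction of 8 points per SD of moderator, i.e. 8/16 = 0.5 SD. Results are expressed as a ratio to the truth.

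**Expected result.** With outcomes missing completely at random and no auxiliary variable, observed participants carry the full slope difference and imputed participants carry none:

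ratio ≈ (1 − f) × 1 + f × 0 = 1 − f

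This gives 0.85 at f = 15% and 0.80 at f = 20%.

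**Simulation.** 3,000 simulated trials per scenario, 5 Bayesian linear-regression imputations each, group-by-moderator term in the analysis model, Monte Carlo standard error about 0.006.

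| Outcome missing | Imputation model | Ratio to truth |
|---|---|---|
| 5% | main effects | 0.96 |
| 15% | main effects | 0.83 |
| 20% | main effects | 0.79 |
| 30% | main effects | 0.69 |
| 15% | with group × moderator | 1.01 |
| 15% | separately by arm | 1.00 |

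In the 15% main-effects run the complete-data estimate was itself 0.987 of the truth by chance; 0.831 / 0.987 = 0.84, in line with the formula. With missingness depending on the moderator at a nominal 15%, the ratio was 0.80, so the missing fraction is not a strict ceiling.

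**Other KOOS-child visits as auxiliaries.** Table 11 schedules KOOS-child at months 0, 1, 2, 3, 5, 8 and later.
- At 15% missing, with one fully observed auxiliary that shares the whole interaction, main-effects ratios were 0.90, 0.93, 0.96 and 0.98 for residual correlations of 0.3, 0.5, 0.7 and 0.9.
- With one auxiliary sharing half or all of the interaction, further runs gave 0.88–0.95 at 15% missing and 0.84–0.92 at 20%. That is shrinkage of 5–12% and 8–16%.
- If the auxiliary carries none of the interaction, the ratio returns to 0.85 (15% missing) and 0.79 (20% missing).
- If the auxiliary (residual correlation 0.6) is also missing for some of those without a month-5 score, the ratio at 15% missing falls from 0.93 (never missing) to 0.89 (half), 0.86 (two-thirds) and 0.85 (all).

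**Moderator missing instead of outcome.** With 15% of moderator values missing, main-effects imputation gave 0.88, and adding the product with the outcome gave 0.97.

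**The case against.** The strongest reply has four parts.

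1. **The text is silent.** A reader might infer that the plan excludes treatment interactions. It does not: all three model families can hold product terms, and mice can be run by arm. This stands, and the point is therefore one of missing specification. Silence still matters, because following the section as written gives main effects.

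2. **The size is not universal.** A reader might infer that every moderator estimate shrinks by the missing fraction. The documents do not support that. The plan puts repeated KOOS-child scores into the imputation, and these can carry part of the interaction; a moderator with no true interaction is not shrunk at all. This stands too, but the rescue is not assured. Two of the three pilot dropouts ceased replying or attending, so neighbouring visits may be missing as well, and the plan does not impute variables outside the analysis.

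3. **The missing fraction may be lower.** Dropout is not the same as a missing month-5 questionnaire. The retention section offers questionnaire-only follow-up, two reminders and a telephone call. This stands: 15% and 20% are scenarios.

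4. **The practical gain is modest.** For an assumed interaction of 0.3 SD, the bias is about 0.02–0.05 SD against a sampling SD of about 0.17–0.21. Root-mean-square error was then 0.178 with main-effects imputation and 0.203 by arm (no auxiliary), or 0.178 and 0.194 (sharing auxiliary). At an assumed 0.625 SD it was 0.206 and 0.209 without an auxiliary. By-arm imputation did better (0.196 against 0.206) only when the auxiliary carried no interaction. This stands: the fix removes a one-directional bias and does not generally reduce total error.

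The analyses concerned are also secondary, and mediation is run only if the experimental arm proves superior.

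**Conclusion.** The plan specifies imputation without saying how planned treatment-by-moderator effects will be preserved. Under main-effects imputation, true interactions are biased towards zero. The shrinkage is about the missing fraction when no informative auxiliary is observed (roughly 15–20% under the two dropout figures), and roughly 5–15% when other KOOS-child visits carry part of the interaction. An always-observed, highly correlated visit sharing the whole interaction could bring it down to about 2%; missingness that depends on the moderator could push it somewhat above the missing fraction.

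These sizes assume main-effects implementation, missingness close to the planning or pilot dropout, and a real interaction whose magnitude the documents do not give. A reader might infer that the primary result is at risk. It is not: the primary model contains no group-by-moderator term, and the sample size reproduces. This is an inexpensive improvement to a secondary analysis.

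**What to change.** Add a sentence to the missing-data section: for the moderation analyses, and for the mediation model that includes moderators, the imputation will be compatible with the analysis model. Two routes are adequate:

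- include the planned group-by-moderator product terms in the mice models; or
- run mice separately in each arm, combine the arms within each imputed dataset, fit the analysis model and pool.

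In either case keep the other KOOS-child visits as auxiliaries. Because the plan imputes only analysis variables, it should allow these visits to be imputed when incomplete. The imputation for the primary analysis need not change on this account.

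The cost is a few lines of code and slightly wider intervals for the interactions. By-arm models on about 65 participants need a shorter predictor list and may meet sparse categories, for example in the three-level growth variables and four-grade ultrasound scales of Table 12. Product terms avoid splitting the sample.
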